4.2.4 Supplementary Analyses

The following supplementary analyses will be performed for the primary efficacy endpoints of OS and IRF-assessed PFS in which a different handling rule of intercurrent events is implemented to provide further understanding of the treatment effect.

To assess the impact of the intercurrent event of starting a non-protocol anti-cancer therapy (NPT) prior to a PFS event, the primary analysis of IRF-assessed PFS will be repeated with such intercurrent event handled using a hypothetical strategy, if >5% of participants received NPT prior to a PFS event in either treatment arm. To estimate the estimand that implements this strategy, participants who start an NPT before a PFS event will be censored at the time of the last tumor assessment before the initiation of NPT.

To assess the impact of the intercurrent event of starting an NPT on OS, the primary analysis of OS will be repeated with such intercurrent event handled using a hypothetical strategy if >10% of participants received NPT in either treatment arm. The discounted method uses a “discounted” survival time after NPT usage for patients who received NPT based on a user-specified assumption for the effect in OS. The duration from initiation of NPT to death or censoring date may be discounted according to a range of possible effects on OS of the subsequent NPT (e.g., 10%, 20%, 30%, etc). After adjustments are made for the effect of subsequent NPT on OS, the methods that are outlined for OS in Section [4.2.2](#) will be used for these analyses.

4.2.4.1 Subgroup Analyses for Primary Endpoints

The generalizability of OS and IRF-assessed PFS results when comparing the experimental arm to the control arm will be investigated by estimating the treatment effect in subgroups defined by demographics and prognostic characteristics, including but not limited to: age, sex, race, ethnicity, ECOG performance status at maintenance baseline, smoking status, LDH at maintenance baseline, presence of liver metastases at induction baseline and prior receipt of PCI.

Summaries of OS and IRF-assessed PFS, including unstratified HRs estimated from Cox proportional hazards models and Kaplan-Meier estimates of median OS and PFS, will be provided in forest plots.

4.3 SECONDARY ENDPOINTS ANALYSES

4.3.1 Investigator-Assessed PFS

Investigator-assessed PFS is defined as the time from randomization to the date of first documented disease progression as assessed by the investigator according to RECIST v1.1 or death, whichever occurs first. Participants who have not experienced disease progression and have not died by the clinical cutoff date will be censored at the time of the last tumor assessment. Participants with no tumor assessment after baseline will be censored at the date of randomization.

Investigator-assessed PFS will be analyzed through use of the same methods described for the IRF-assessed PFS analysis (see Section [4.2.2](#)).

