### **8.1.1.1 Radiographic Assessments**

Participants will undergo tumor assessments at induction screening and at maintenance screening. The tumor assessment at induction screening will serve to determine whether participants have SD or partial or complete response following the completion of induction therapy at the time of screening for the maintenance phase. The tumor assessment at maintenance screening will serve as the baseline to determine tumor response per RECIST v1.1 post-randomization.

All participants in the maintenance phase will undergo tumor assessments every 6 weeks ( $\pm 7$  days) for 48 weeks following Day 1 of Cycle 1 of maintenance therapy, regardless of treatment delays. After completion of the Week 48 tumor assessment, tumor assessments are required every 9 weeks ( $\pm 7$  days), regardless of treatment delays. Participants without any radiographic evidence of disease progression 2 years after Cycle 1, Day 1 of the maintenance phase may undergo tumor assessments every 3 months ( $\pm 7$  days) or more frequently if required per local standard of care. Tumor assessments are to be performed until radiographic disease progression per RECIST v1.1 criteria, withdrawal of consent, study termination by the Sponsor, or death, whichever occurs first. Magnetic resonance imaging surveillance of the brain (preferred) or brain CT with contrast every 3–4 months is recommended during Year 1, and every 6 months during Year 2 independent of the use of PCI (NCCN 2021a).

Additional tumor assessments during the induction and maintenance phases will be performed as per local standard of care and as clinically indicated and must also be reported in the study database as unscheduled visits.

Tumor assessments at induction screening, maintenance screening, and subsequent assessments must include computed tomography (CT) scans (with IV contrast, unless contraindicated, and oral contrast as appropriate per institutional standards) of the chest and abdomen. A CT scan, with contrast, of the pelvis is required at induction screening, maintenance screening, and as clinically indicated or as per local standard of care at subsequent response evaluations. Magnetic resonance imaging scans with contrast of the chest, abdomen, and pelvis with a non-contrast CT scan of the chest may be used in participants for whom CT scans with IV contrast are contraindicated (i.e., participants with iodine-based contrast allergy or impaired renal clearance).

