1. INTRODUCTION

The Statistical Analysis Plan (SAP) provides details of the planned analyses and statistical methods for Study GO43104 (IMforte), a Phase III, randomized, open-label, multicenter study of lurbinectedin in combination with atezolizumab compared with atezolizumab as maintenance therapy in participants with extensive-stage small-cell lung cancer (ES-SCLC) following first-line induction therapy with carboplatin, etoposide and atezolizumab. The background of the study can be found in the study protocol.

The analyses described in this SAP will supersede those specified in Protocol GO43104 for the purposes of a regulatory filing.

There are no changes to the planned analyses described in the protocol.

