2.2.2 Overall Survival

The sample size determination is based on the number of events required to demonstrate efficacy with regard to OS in the FAS. The estimate of the number of events required is based on the following assumptions:

- 1:1 randomization ratio
- Two-sided significance level of 0.049 for the comparison of OS
- Approximately 85% power to detect an hazard ratio (HR)= 0.71 in OS, corresponding to an improvement in median OS from 12.5 months to 17.6 months in the FAS
- One planned interim analysis for OS at approximately 68% of the information fraction, with the stopping boundary determined by the Hwang-Shih-DeCani alpha spending function with the gamma parameter of -1.5 ([Hwang et al. 1990](#))
- Dropout rate of 5% over 24 months for each treatment arm for OS

With these assumptions, the final OS analysis will occur when approximately 323 deaths (72% of █ randomized participants) have been observed in the FAS. With these assumptions, the minimum detectable difference (MDD) in HR is approximately 0.793 for the final OS analysis. The final OS analysis is expected to occur approximately 41 months after the first patient is randomized.

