2.2.3 IRF-assessed PFS

The primary IRF-assessed PFS analysis will be conducted at the time of the OS interim analysis when approximately 219 deaths in the FAS have been observed or when the minimum follow-up has been completed, whichever occurs later. The minimum follow-up is defined as 5 months after the target sample size of 450 participants has been randomized, or 5 months after the last participant has been randomized in case the final sample size is lower than 450 participants.

At the time of the OS interim analysis, it is estimated that approximately 392 IRF-assessed PFS events in the FAS will have occurred. This number of events provides more than 99% power to detect an HR= 0.5 in IRF-assessed PFS at a 2-sided significance level of 0.001, based on the following assumptions:

- 1:1 randomization ratio
- Median PFS of 2.6 months in the atezolizumab arm and 5.2 months in the atezolizumab + lorbinecetin arm (corresponding to a target HR=0.5)
- Dropout rate of 5% over 12 months for PFS
- No interim analysis for PFS

With these assumptions, the MDD in HR is approximately 0.72 for the IRF-assessed PFS analysis in the FAS.

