4.2.2 Main Analytical Approach for Primary Estimands

For IRF-assessed PFS, participants who have not experienced disease progression and have not died by the clinical cutoff date will be censored at the time of the last tumor assessment. Participants who have no tumor assessment after baseline and have not died by the clinical cutoff date will be censored at the date of randomization.

For OS, participants who are not reported as having died by the clinical cutoff date will be censored at the date when they were last known to be alive. Participants who do not have information after baseline will be censored at the date of randomization.

Participants who are lost to follow-up will be censored at the last date they were known to be alive for the primary analysis of OS.

Each of the primary endpoints will be compared between two treatment arms based on the stratified log-rank test. The HR will be estimated with use of a stratified Cox regression model, including two-sided 95% confidence intervals (CIs). The stratification factors will be those used for randomization (as listed in Section 1.2.1). The Kaplan-Meier methodology will be used to estimate the median IRF-assessed PFS and median OS for each treatment arm, and Kaplan-Meier curves will be constructed to provide a

visual description of the difference between treatment arms. The Brookmeyer-Crowley methodology will be used to construct the 95% CIs for the median IRF-assessed PFS and median OS for each treatment arm ([Brookmeyer and Crowley 1982](#)). Results from an unstratified analysis will also be provided.

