4.3.4 Progression-Free Survival and Overall Survival Rates at Landmark Timepoints

The IRF-assessed and investigator-assessed PFS rates at 6 months and at 12 months after randomization will be estimated with use of the Kaplan-Meier methodology for each treatment arm, along with 95% CIs calculated with use of the standard error derived from Greenwood's formula. The 95% CI for the difference in PFS rates between the two treatment arms will be estimated with use of the normal approximation method.

Similar analyses will be performed for the OS rates at 12 months and 24 months after randomization.

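### SAP 4.3.1 drops the alive-at-cutoff condition, so investigator-assessed PFS could censor a death before any scan at Day 0

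*SAP*

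**What the plan says.** The SAP gives two different Day 0 censoring rules for the two PFS readings.

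- **IRF-assessed PFS (SAP 4.2.2):** Day 0 censoring is limited to those who lack any post-baseline scan and are also alive at the cutoff.
- **Investigator-assessed PFS (SAP 4.3.1):** "Participants with no tumor assessment after baseline will be censored at the date of randomization".

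SAP 4.3.1 also defines the endpoint as progression or death. Its general censoring sentence, at the last tumor assessment, applies only to participants who are alive and progression-free. It closes by pointing back to 4.2.2: "Investigator-assessed PFS will be analyzed through use of the same methods described for the IRF-assessed PFS analysis".

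SAP 4.3.4 carries the endpoint into the landmark analysis: "The IRF-assessed and investigator-assessed PFS rates at 6 months and at 12 months after randomization will be estimated".

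Protocol 9.4.2.1 (IRF) and 9.4.3.1 (investigator) both use the unconditioned sentence. The SAP therefore added the survival condition for the IRF reading only. Its Introduction says "The analyses described in this SAP will supersede those specified in Protocol GO43104 for the purposes of a regulatory filing", and also declares that nothing in the planned analyses has changed from the protocol.

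**The concern.** Taken alone, the 4.3.1 sentence censors at randomization a participant who dies before any post-baseline scan. That conflicts with the section's own event definition and with its statement that the 4.2.2 methods apply. The protocol cannot settle the matter, because it has the same unconditioned wording and the SAP takes precedence for the filing.

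If the sentence were programmed literally, one death would be an event in IRF-assessed PFS and a Day 0 censoring in investigator-assessed PFS. In an open-label trial, readers will compare the two to look for assessment bias, and part of any discordance would then have nothing to do with reading images. The investigator-assessed 6- and 12-month rates would also be too high in both arms. Protocol 4.2 lists pre-defined censoring rules among the safeguards for the open-label design, and a rule open to two programs is not fully pre-defined. The sensitivity analyses in SAP 4.2.3 cover OS and IRF-assessed PFS only, so none of them would expose the problem.

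**Working it through.** The plan gives no event count or power for investigator-assessed PFS, so there is no stated figure to reproduce. The steps below size the difference between the two readings.

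**Inputs**
- OS medians of 12.5 and 17.6 months (SAP 2.2.2: "corresponding to an improvement in median OS from 12.5 months to 17.6 months in the FAS").
- 450 participants, 225 per arm at 1:1 (SAP 2.2.3: "5 months after the target sample size of 450 participants has been randomized").
- PFS medians of 2.6 and 5.2 months (SAP 2.2.3). They are planned for the IRF reading; applying them to the investigator reading is my assumption.
- Scans every 6 weeks, ±7 days (Protocol 8.1.1).
- Exponential times, also an assumption.

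**Step 1: deaths before the first scan.** P = 1 − 2^(−w/median), with w in months = weeks/4.348. Week 6 is 1.380 months.
- Control: 1 − 2^(−1.380/12.5) = 7.4%, and × 225 = 16.6.
- Arm A: 1 − 2^(−1.380/17.6) = 5.3%, and × 225 = 11.9.
- Total: 28.5.

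| First scan at | Planned OS hazard | Half that hazard |
|---|---|---|
| Week 5 | 23.9 | 12.1 |
| Week 6 | 28.5 | 14.5 |
| Week 7 | 33.0 | 16.8 |

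The half-hazard column allows for entrants being selected as non-progressing. All of these counts are upper ranges, because some of these participants would have had an unscheduled scan. Protocol 8.1.1.1 says such scans "must also be reported in the study database as unscheduled visits".

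**Step 2: landmark rates.** Participants censored at Day 0 leave every risk set. The Kaplan-Meier estimate then becomes S(t)/(1 − p), where p is the Week 6 probability from Step 1.

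| | Death counted | Literal rule |
|---|---|---|
| 6 months, control | 20.2% | 0.202/(1 − 0.074) = 21.8% |
| 6 months, Arm A | 44.9% | 0.449/(1 − 0.053) = 47.4% |
| 6 months, difference | 24.7 points | 25.6 points |
| 12 months, control | 4.1% | 4.4% |
| 12 months, Arm A | 20.2% | 21.3% |
| 12 months, difference | 16.1 points | 16.9 points |

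The differences are computed before rounding.

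**Step 3: hazard ratio by simulation.** I ran 2,000 trials of 225 per arm with the PFS medians above, 6-week scans ±7 days, an assumed administrative cutoff uniform on 5 to 30 months, and a Cox model.

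| Death hazard | HR, death counted | HR, literal | Events, death counted | Events, literal |
|---|---|---|---|---|
| Planned | 0.507 | 0.494 | 404 | 376 |
| Half of planned | 0.501 | 0.495 | 403 | 388 |

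Power at two-sided 0.05 was about 100% throughout. The HR drifts towards Arm A because the planned effect on death (HR 0.71) is weaker than the planned effect on PFS (HR 0.5), so dropping early deaths removes the less favourable component.

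**Step 4: what a larger shift would need.** Doubling only Arm A's death hazard gives 0.529 against 0.472. This is a pure assumption: it implies an Arm A median OS of 17.6/2 = 8.8 months and an OS HR of 12.5/8.8 = 1.42, the reverse of the plan.

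**The case against.** The strongest reply is that SAP 4.3.1 largely resolves itself. Death is in the definition, the preceding sentence restricts censoring to living participants, and the disputed sentence reads naturally as the sub-case with no scan date to censor at. The cross-reference to 4.2.2 then supplies the missing condition. The SAP's declaration of no changes from the protocol also suggests that the sponsor treats the short and long wordings as equivalent. The endpoint carries no alpha and the effect is small. Finally, the Version 8 rationale in the protocol says the final OS cutoff has been reached and some analyses are complete, so editing the SAP now may come after results are known.

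Much of this stands. Counting the deaths is the better reading, and nothing in the documents shows that they were in fact censored. The doubled-hazard case has no basis in the documents. The timing argument favours a programming check over a text edit.

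It does not remove the defect. The SAP added the condition for one PFS reading and left it out for the other, and a programmer could take that difference as deliberate. The declaration of no changes is weak evidence of intent, since the SAP visibly altered the protocol's wording in 4.2.2.

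**Conclusion.** The concern holds as an inconsistency in a stated rule, and it should be fixed. The omission itself is certain; whether it reached the programs cannot be known from the documents.

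The consequence is confined to investigator-assessed PFS and its 6- and 12-month rates. At planned rates the literal rule moves the HR by 0.013 (0.507 − 0.494) and widens the 6-month difference by 0.9 points. At half the death hazard the HR moves by 0.006 (0.501 − 0.495). No conclusion about efficacy would turn on this.

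The sizes rest on exponential survival at the planned medians and on no unscheduled scans before death. The actual direction and size depend on how early deaths without a scan split by arm, which the documents do not give.

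**What to change.** 1. Check the programs for investigator-assessed PFS and its landmark rates. A participant with no post-baseline assessment should be censored at randomization only if not known to have died by the cutoff. A death without a scan should be an event on the date of death. If the literal rule was used, rerun these analyses.
2. Put the survival condition from SAP 4.2.2 into SAP 4.3.1 or, if the SAP is closed, state the rule in the CSR.
3. Note in SAP Section 1 or the CSR that this clarifies the protocol text.
4. Align Protocol 9.4.2.1 and 9.4.3.1 only if the protocol is amended for another reason.

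The cost is one clause or a CSR note, plus a programming check. It requires no new data, no additional participants and no protocol amendment for this alone.

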4.3.2 Confirmed Objective Response Rate

A confirmed objective response is defined as either a complete response (CR) or a partial response (PR) on two consecutive occasions ≥ 4 weeks apart after randomization, as determined by the IRF according to RECIST v1.1. Participants not meeting these criteria, including participants without any post-baseline tumor assessment, will be considered non-responders.

The analysis set for confirmed objective response rate (ORR) will be the FAS with measurable disease at baseline. An estimate of confirmed ORR and its 95% CI will be calculated with use of the Clopper Pearson method for each treatment arm. Confidence intervals for the difference in confirmed ORRs between the two treatment arms will be determined with use of the normal approximation to the binomial distribution.

The investigator-assessed confirmed ORR will also be analyzed through the same methods as described above.

4.3.3 Duration of Response

Duration of response (DOR) will be assessed in participants who had a confirmed objective response as determined by the IRF according to RECIST v1.1 in the FAS. Duration of response is defined as the time interval from the date of the first occurrence

of a documented confirmed objective response until the first date of progressive disease (PD) as determined by the IRF according to RECIST v1.1 or death is documented, whichever occurs first. Participants who have not progressed and who have not died at the time of analysis will be censored at the time of the last tumor assessment date. Duration of response is based on a non-randomized subset of participants (specifically, participants who achieved a confirmed objective response); therefore, formal hypothesis testing will not be performed for this endpoint. Comparisons between treatment arms will be made for descriptive purposes.

Duration of response (for participants with confirmed objective response), as determined by the investigator according to RECIST v1.1, will also be analyzed.

The methodologies detailed for the PFS analysis will be used for the DOR analysis.

4.3.4 Progression-Free Survival and Overall Survival Rates at Landmark Timepoints

The IRF-assessed and investigator-assessed PFS rates at 6 months and at 12 months after randomization will be estimated with use of the Kaplan-Meier methodology for each treatment arm, along with 95% CIs calculated with use of the standard error derived from Greenwood's formula. The 95% CI for the difference in PFS rates between the two treatment arms will be estimated with use of the normal approximation method.

Similar analyses will be performed for the OS rates at 12 months and 24 months after randomization.

4.3.5 Incidence and Severity of Adverse Events

The secondary safety objective will be assessed through summaries of the incidence and severity of treatment-emergent adverse events (AEs) in the SAS.

Verbatim description of adverse events will be mapped to the Medical Dictionary for Regulatory Activities (MedDRA) thesaurus terms. Severity for all adverse events will be graded by the investigator according to the National Cancer Institute Common Terminology Criteria for Adverse Events (NCI CTCAE) v5.0. Severity for Cytokine release syndrome (CRS) will also be graded by the investigator according to the American Society of Transplantation and Cellular Therapy (ASTCT) consensus grading scale. All adverse events will be summarized by treatment arm and NCI CTCAE grade. Cytokine release syndrome will also be summarized by treatment arm and the ASTCT consensus grade. All adverse events, Grade 3-4 adverse events, serious adverse events, adverse events leading to death, adverse events of special interest, adverse events leading to treatment interruption/modification and adverse events leading to study treatment discontinuation that occur on or after the first dose of study treatment (i.e., treatment-emergent adverse events) will be summarized by preferred term, system organ class, and severity grade. For events of varying severity, the highest grade will be used in the summaries. Multiple occurrences of the same event in the same patient will

be counted once at the maximum severity. Deaths and cause of death will be summarized.

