### **8.3.1 Time Period and Frequency for Collecting Adverse Event and Serious Adverse Event Information**

After informed consent has been obtained but prior to initiation of study drug, only serious adverse events caused by a protocol-mandated intervention should be reported (see [Appendix 3](#)). The paper Clinical Trial Adverse Event/Special Situations Form provided to investigators should be completed and submitted to the Sponsor or its designee immediately (i.e., no more than 24 hours after learning of the event), either by faxing or by scanning and e-mailing the form using the fax number or e-mail address provided to investigators. All other medical occurrences that begin before the start of study treatment will be recorded on the General Medical History and Baseline Conditions eCRF, not the Adverse Event eCRF.

All adverse events will be reported from the start of treatment until 30 days after the final dose of study treatment or until start of new systemic anti-cancer therapy, whichever occurs first. Serious adverse events and adverse events of special interest will be reported from the start of study treatment until 90 days after the final dose of study treatment or until start of new systemic anti-cancer therapy, whichever occurs first. Serious adverse events and adverse events of special interest considered related to prior exposure to study treatment will be reported indefinitely.

All serious adverse events will be recorded and reported to the Sponsor or designee immediately and under no circumstance should this exceed 24 hours, as indicated in [Appendix 3](#). The investigator will submit any updated serious adverse event data to the Sponsor within 24 hours of it being available.

Investigators are not obligated to actively seek adverse event or serious adverse event information after conclusion of study participation. However, if the investigator learns of any serious adverse event, including a death, at any time after a participant has been discharged from the study, and he or she considers the event to be reasonably related to the study treatment or study participation, the investigator must promptly notify the Sponsor.

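### Adverse events are compared between arms only as crude incidence, although the planned PFS effect and treatment to progression imply longer adverse-event observation in Arm A

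*SAP*

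**What the plan says.** The secondary safety objective (SAP Table 2) compares lurbinectedin plus atezolizumab with atezolizumab, and its endpoint is the incidence and severity of AEs. SAP 4.3.5 delivers this as counts by arm, term and grade: "All adverse events will be summarized by treatment arm and NCI CTCAE grade". A participant with repeated occurrences of an event is counted once, at the worst grade. Protocol 9.4.3.5 reads the same way. SAP 4.5.1 summarizes duration of exposure, dosage and dose intensity, but does not use exposure as a denominator for AEs. SAP 4.3.5, 4.5.1 and 4.5.2 are readable in full and contain no person-time rate, time-to-first-event, cumulative-incidence or fixed-window AE analysis.

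Three other places determine how long AEs are observed:

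- SAP 2.2.3 assumes "Median PFS of 2.6 months in the atezolizumab arm and 5.2 months" in the combination arm.
- Protocol 8.1.1 continues treatment to radiographic progression, unacceptable toxicity or the participant's decision. Section 7.1 adds other reasons for stopping.
- Protocol 8.3.1: "All adverse events will be reported from the start of treatment until 30 days after the final dose of study treatment". For serious AEs and AESIs the period is 90 days. Both periods end earlier if a new systemic anti-cancer therapy starts.

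**The concern.** A crude proportion depends on the event hazard and on the time during which an event can be recorded. If the trial performs as planned, participants in Arm A progress later, stay on treatment longer and are observed for AEs longer. Part of the efficacy benefit would then be displayed as added toxicity.

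The stake is greatest for immune-mediated events. Protocol 2.3 and Appendix 6 (A6-1.3) state that lurbinectedin is not expected to affect them, and atezolizumab may continue after lurbinectedin stops (A6-2.1). A higher crude AESI percentage in Arm A would be expected from observation time alone, so the crude tables cannot tell whether that expectation was met. The exposure summary would show that the arms differ in duration. It would not let a reader adjust, because person-time to first event cannot be recovered from it.

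**Working it through.** **1. The plan's own PFS figures.** Inputs from SAP 2.2.3: 392 events, HR 0.5, two-sided alpha 0.001, 1:1 allocation.

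- Power = Φ(√392/2 × ln 2 − 3.291) = Φ(6.862 − 3.291) = 0.9998. The SAP states: "This number of events provides more than 99% power to detect an HR= 0.5 in IRF-assessed PFS at a 2-sided significance level of 0.001".
- Minimum detectable HR = exp(−2 × 3.291/√392) = 0.717. The SAP states: "the MDD in HR is approximately 0.72 for the IRF-assessed PFS analysis in the FAS".

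Both reproduce, so the planned medians are a sound reading of the design effect.

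**2. Observation time.** Assume exponential time on treatment with median equal to the planned PFS median. The stopping rate is u = ln 2/median: 0.2666 per month (B) and 0.1333 (A). Mean AE observation is 1/u plus the post-dose window.

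| Period | B (months) | A (months) | Ratio A/B |
|---|---|---|---|
| To progression | 3.75 | 7.50 | 2.00 |
| Plus 30 days | 4.74 | 8.49 | 1.79 |
| Plus 90 days | 6.71 | 10.46 | 1.56 |

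If treatment also stops for other reasons at an assumed 5% per month in both arms, the on-treatment ratio is 1.73, and 1.55 with the 30-day window. Windows cut short by new therapy in both arms move the ratio back towards the on-treatment value.

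**3. Crude incidence with no true difference.** With the same constant hazard λ in both arms and window w, crude incidence = 1 − [u/(u + λ)] × exp(−λw). The documents give no λ, so it is solved for an assumed control incidence and then applied to Arm A.

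Example with control 20% and w = 30/30.44 = 0.986 months, for which λ = 0.0505 per month:

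- B: 1 − (0.2666/0.3171) × 0.951 = 20.0%
- A: 1 − (0.1333/0.1838) × 0.951 = 31.0%

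| Control incidence | A, 30-day window | Risk ratio | A, 90-day window | Risk ratio |
|---|---|---|---|---|
| 10% | 16.6% | 1.66 | 14.8% | 1.48 |
| 20% | 31.0% | 1.55 | 28.2% | 1.41 |
| 30% | 43.5% | 1.45 | 40.4% | 1.35 |

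The 90-day columns apply to serious AEs and AESIs. With the assumed 5% per month of other stopping, the 90-day risk ratios fall to 1.33 to 1.25.

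**4. Which denominator works.** First events divided by true time at risk give equal rates when hazards are equal. At λ = 0.05 per month both arms show 5.0 per 100 patient-months, while crude incidence is 19.8% (B) against 30.8% (A).

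Dividing instead by mean exposure duration (3.75 and 7.50 months) simply halves the risk ratios above: 0.83 to 0.73 (30-day) and 0.74 to 0.67 (90-day), where the true ratio is 1.00. The numerator includes post-dose events but the denominator omits post-dose time. Stopping exposure at the first event still gives about 0.90 and 0.78.

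**5. Early events.** Suppose onset at 0.5 month, crude incidence 20% (A) against 10% (B), and the 30-day observation means for participants without an event. Person-time per participant is 0.2 × 0.5 + 0.8 × 8.49 = 6.89 months (A) and 0.1 × 0.5 + 0.9 × 4.74 = 4.32 months (B). The rate ratio is (0.20/6.89)/(0.10/4.32) = 1.25, although the crude ratio is 2.0.

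**The case against.** Several points on the other side stand.

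- A reader might infer that the plan expects twice the time on treatment. It does not say so. The 2.6 and 5.2 months are IRF-assessed PFS medians, treatment can end before progression, and either drug can stop alone. Two is an upper-end inference, and AE observation differs by less because the same post-dose window is added in both arms.
- The 30-day figures do not apply to serious AEs and AESIs. The smaller 90-day figures do.
- A person-time rate is not neutral. Step 5 shows that it dilutes early toxicity, and the Protocol describes early lurbinectedin toxicity: Grade 3 or 4 neutropenia with a median onset of 15 days (4.3.5). A rate alone could hide a real excess.
- The endpoint is defined as incidence and severity, and the SAP reports exactly that. The tables are descriptive, SAP 4.3.5 plans no between-arm AE test, and exposure duration is reported, so the imbalance will be visible.

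These points limit the size and shape the remedy. They do not remove the gap: nothing in the readable AE and exposure sections separates a higher hazard from longer observation.

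**Conclusion.** The point holds as a worthwhile improvement to the descriptive safety analysis. Under the planned PFS effect, equal hazards would produce a visibly higher crude incidence in Arm A, with the risk ratios in step 3. This rests on exponential time on treatment at the planned PFS medians, a constant hazard common to both arms, and assumed control incidences of 10% to 30%. Other stopping reasons reduce the effect, and a smaller observed PFS difference would shrink it.

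A reader might go further and treat any crude excess in Arm A as an artefact. The documents do not support that. Events confined to the first cycles are hardly affected by later follow-up, and a true lurbinectedin excess would be overstated rather than created. No primary or alpha-controlled conclusion is affected.

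**What to change.** Keep the crude tables. In SAP 4.3.5, add by arm:

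1. **First events per 100 patient-years at risk** for all AEs, Grade 3-4 AEs, serious AEs, AEs leading to discontinuation and AESIs. Time at risk runs from the first maintenance dose to the earliest of first event, end of the applicable 30- or 90-day collection window, new systemic anti-cancer therapy, death or data cutoff. State that the exposure duration in SAP 4.5.1 is not the denominator. Name the first maintenance dose explicitly, because SAP 1.1 defines study treatment to include induction.
2. **Cumulative incidence of first event over time, with competing events,** for AESIs and Grade 3-4 AEs, because a rate assumes a roughly constant hazard.

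State that both are to be read beside the crude tables. The cost is a few extra descriptive tables and curves. AE and dosing dates are already collected, and no test, alpha or new data are needed.
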